2.4.5.3 Deaths

The following summaries of deaths will be generated for the safety population.

- Number (%) of patients who died by study period (on-study, on-treatment, post-study)
- Deaths in nonrandomized patients or randomized but not treated patients

TEAEs leading to death (death as an outcome on the eCRF AE page as reported by the investigator) by primary SOC, HLT, HLT, and PT, showing number (%) of patients, sorted by internationally agreed order of SOC and alphabetic order of HLT, HLT, and PT.

The summaries will be provided by treatment group for the 26-week randomized treatment period and for FRC group for the whole study treatment period including the 26-week single-arm extension period, respectively.

2.4.5.4 Analyses of laboratory variables

Laboratory parameters will be grouped and summarized by biological function as described in [Section 2.1.4.4](#). The summaries will be provided by treatment group for the 26-week randomized treatment period and for FRC group for the whole study treatment period including the 26-week single-arm extension period, respectively.

Descriptive statistics (N, mean, median, SD, minimum, and maximum) will be used to summarize results and changes from baseline of all laboratory parameters. Summaries will be presented by treatment group using baseline values, observed values from scheduled visits and last on-treatment values. In addition, descriptive statistics will also be presented separately for the post-treatment period.

The number (%) of patients with PCSAs (list provided in [Appendix A](#)) at any time during the on-treatment period will be summarized by biological function and treatment group for each laboratory parameter, except calcitonin and the albumin/creatinine ratio, whatever the baseline level and/or according to the following baseline status categories:

- Normal/Missing,
- Abnormal according to PCSA criterion or criteria.

For calcitonin and the albumin/creatinine ratio, no PCSA criterion is defined. Similar summaries using the pre-defined categories will be provided for the on-treatment period. The pre-defined categories are, for calcitonin \leq ULN, $>$ ULN - 20 ng/L, \geq 20 - $<$ 50 ng/L, and \geq 50 ng/L (Note that ng/L is the standard international unit and is equivalent to pg/mL); and for albumin/creatinine ratio $<$ 30 μ g/mg creatinine [Normal], \geq 30 to $<$ 300 μ g/mg creatinine [Microalbuminuria], and \geq 300 μ g/mg creatinine [Macroalbuminuria]. For calculated estimated eGFR, the classification according to Food and Drug Administration (FDA) guidance published on March 2010 will be used as the PCSA criterion: $<$ 15 mL/min/1.73m² [End stage renal disease], \geq 15 to $<$ 30 mL/min/1.73m² [Severe decrease in GFR], \geq 30 to $<$ 60 mL/min/1.73m² [Moderate decrease in GFR], \geq 60 to $<$ 90 mL/min/1.73m² [Mild decrease in GFR], and \geq 90 mL/min/1.73m² [Normal].

All measurements collected during the on-treatment period, including values from unscheduled visits, will be considered for the PCSA summaries. These summaries will include patients in the safety population who have at least 1 assessment performed during the on-treatment period. When a PCSA definition involves a change from baseline value, patients must also have a baseline value to be included in the summaries, and when required by the definition of the abnormality, patients must also have available laboratory normal ranges.

For some parameters, such as liver enzymes, the lower limit of normal (LLN) is not considered clinically relevant, and values below this limit are considered normal. When there are multiple PCSA criteria for a specific parameter (eg, ALT), the patient will be counted once during the on-treatment period for the specific parameter in question under the worst/maximum PCSA category.

PCSA summaries (or similar summaries using the pre-defined categories for calcitonin and albumin/creatinine ratio) will also be presented separately for the post-treatment period.

For parameters for which no PCSA criterion is defined, similar table(s) using the normal ranges will be provided.

A listing of patients with at least 1 post-baseline PCSA (or out of normal range when no PCSA criterion is defined) will be provided and will display the entire patients' profile across time for all parameters belonging to the corresponding biological function. Individual data listings will include flags when applicable:

- Baseline values will be flagged "B".
- Normal laboratory ranges, available for most laboratory parameters, will be identified as ULN and LLN. Baseline, and individual data will be flagged "L" if the value is below the LLN and will be flagged "H" if it is above the ULN.
- Laboratory PCSA criteria will be used for the corresponding laboratory parameters. Values reaching a PCSA limit will be flagged (+, ++, -, or – depending upon the direction and level of the abnormality). Flags for WBC and differential counts will be determined using data expressed in international units.

For parameters whose PCSA criteria are multiples of the ULN, the parameter's value will also be expressed as a multiple of the ULN in the individual data provided.

Drug-induced liver injury

The liver function tests, namely AST, ALT, ALP, and total bilirubin, are used to assess possible drug-induced liver toxicity. The proportion of patients with PCSA values at any post-baseline visit by baseline status will be displayed by treatment group for each parameter. The proportion of patients with PCSA values at any post-baseline visit will also be displayed by duration of exposure for each treatment group (only if a tabulation summary is necessary).

A listing will be provided for possible Hy's law cases identified by treatment group (eg, patients with any elevated ALT > 3 x ULN, and associated with an increase in total bilirubin > 2 x ULN) with liver related TEAEs, ALT, AST, ALP, total bilirubin, and the following complementary parameters if available: conjugated bilirubin and prothrombin time/INR, creatine phosphokinase, serum creatinine, complete blood count, immunoglobulin M (IgM) antibodies to Hepatitis A virus, IgM antibodies to Hepatitis B core antigen, antibodies to Hepatitis C Virus, and Hepatitis C ribonucleic acid, IgM antibodies to Cytomegalovirus, and IgM antibodies to Hepatitis E virus, auto-antibodies: anti-nuclear, anti-deoxyribonucleic acid, anti-smooth muscle, Epstein-Barr virus, herpes viruses, and anti-liver/kidney microsomes.

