- Patients with conditions/concomitant diseases precluding their safe participation in this study (eg, malignant tumor within 5 years prior to screening visit (V1), major systemic diseases, presence of clinically significant diabetic retinopathy or presence of macular edema likely to require treatment within the study period);
- Impossibility to meet specific protocol requirements (eg, scheduled visits, patients unable to fully understand patient's study documents and to complete them);
- Patient is uncooperative or has a condition that could lead to non-compliance with the study procedures (eg, patient unable or unwilling to do self-injections or blood glucose monitoring using the sponsor-provided blood glucose meter at home);
- Patient is the Investigator or any Sub-Investigator, research assistant, pharmacist, study coordinator, other staff or relative thereof directly involved in the conduct of the protocol;
- Patients with short life expectancy;
- Requirement for concomitant treatment that could bias primary evaluation.

E 17. Laboratory findings at the screening visit:

- Fasting Plasma Glucose (FPG) >250 mg/dL (13.9 mmol/L);
- Amylase and/or lipase: >3 times the upper limit of the normal (ULN) laboratory range,
- Alanine aminotransferase (ALT) or aspartate aminotransferase (AST): >3 ULN;
- Total bilirubin >1.5 ULN (except in case of Gilbert's syndrome);
- Calcitonin \geq 20 pg/mL (5.9 pmol/L);
- Hemoglobin <10.5 g/dL or neutrophils <1,500/mm³ or platelets <100,000/mm³;
- Positive test for Hepatitis B surface antigen (HBsAg) and/or Hepatitis C antibody (HCAb);
- Positive serum pregnancy test in females of childbearing potential.

E 18. Patient who has renal function impairment with estimated glomerular filtration rate (GFR) <30 mL/min/1.73m² (using the MDRD [[Appendix A](#)]) or end-stage renal disease;

E 19. Any technical/administrative reason that makes it impossible to randomize the patient in the study;

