- Percentage of patients with GLP-1 receptor agonist use by type [QD/BID formulations (Victoza® or Byetta®), QW formulations (Bydureon®, Tanzeum®, or Trulicity®)] at screening;
- Daily dose of GLP-1 receptor agonist (Victoza® or Byetta®) at baseline, or weekly dose of GLP-1 receptor agonist (Bydureon®, Tanzeum, or Trulicity®) at baseline;
- Percentage of patients who used pioglitazone at screening (data from e-CRF);
- Percentage of patients who used SGLT2 inhibitor at screening (data from e-CRF);
- Duration of metformin treatment (years) derived as: (Date of informed consent – Date of first dose of metformin + 1)/365.25;
- Daily dose of metformin (mg) at baseline;
- Daily dose of pioglitazone (mg) at baseline (if used);
- Daily dose of SGLT2 inhibitor (canagliflozin, empagliflozin or dapagliflozin) at baseline (if used);
- Categorized daily dose of metformin at baseline (<1500, ≥1500 to <2500, ≥2500 to <3000, ≥3000 mg);
- Baseline diabetic microvascular complications (Yes, No) (ie, diabetic retinopathy, diabetic proliferative retinopathy, diabetic neuropathy, and diabetic nephropathy);
- Baseline urine albumin/creatinine ratio categories (<30 mg/g [Normal], ≥30 to <300 mg/g [Microalbuminuria], and ≥300 mg/g [Macroalbuminuria]);
- Estimated Glomerular Filtration Rate (eGFR) at screening (ml/min/1.73m²);
- eGFR categories at screening (<15 ml/min/1.73m² [End stage renal disease], ≥15 to <30 ml/min/1.73m² [Severe decrease in GFR], ≥30 to <60 ml/min/1.73m² [Moderate decrease in GFR], ≥60 to <90 ml/min/1.73m² [Mild decrease in GFR], and ≥90 ml/min [Normal]).

Baseline efficacy variables

The baseline efficacy variables include:

- HbA1c;
- During standardized meal test:
 - 2-hour postprandial plasma glucose (PPG) and glucose excursion;
 - C-peptide under fasting (30 minutes prior to the meal test before IMP administration if IMP is injected before breakfast), just before the start of the standardized meal (0 minute), 30 minutes, 1-hour, 1.5-hour, and 2-hour postprandial conditions;

Note: 2-hour plasma glucose excursion= 2-hour post prandial plasma glucose value – plasma glucose value obtained 30 minutes prior to the start of meal and before IMP administration if IMP is injected before breakfast. C-peptide under 1.5-hour postprandial condition is only for patients enrolled after the approval of Protocol Amendment 1.

- 7-point (average and each time point) SMPG;
- Body weight;
- Fasting plasma glucose (by central laboratory).

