Handling of adverse events with missing or partial date/time of onset

Missing or partial missing AE onset dates and times will be imputed so that if the partial AE onset date/time information does not indicate that the AE started prior to treatment or after the on-treatment period, the AE will be classified as treatment-emergent. No imputation of AE end dates/times will be performed. These data imputations are for categorization purpose only and will not be used in listings. No imputation is planned for date/time of AE resolution.

Handling of adverse events when date and time of first IMP administration is missing

When the date and time of the first IMP is missing, all AEs that occurred after or on the day of randomization and before or on the day of last dose plus 3 days for daily formulation and 9 days for weekly formulation should be considered as TEAEs. The exposure duration should be kept as missing. The last dose intake should be clearly identified in the eCRF and should not be approximated by the last returned package date.

Handling of missing assessment of relationship of adverse events to IMP/NIMP/study procedures

If the assessment of the relationship to IMP/NIMP/study procedures is missing, the relationship to IMP/NIMP/study procedures has to be assumed and the AE considered as such in the frequency tables of possibly related AEs, but no imputation should be done at the data level.

Handling of missing severity/grades of adverse events

If the severity is missing for one of the treatment-emergent occurrences of an AE, the maximal severity on the remaining occurrences will be considered. If the severity is missing for all the occurrences, a “missing” category will be added in summary table.

Handling of potentially clinically significant abnormalities

If a patient has a missing baseline he will be grouped in the category “normal/missing at baseline.”

For PCSAs with 2 conditions, one based on a change from baseline value or a normal range and the other on a threshold value, with the first condition being missing, the PCSA will be based only on the second condition.

For a PCSA defined on a threshold and/or a normal range, this PCSA will be derived using this threshold if the normal range is missing; e.g., for eosinophils the PCSA is >0.5 GIGA/L or $>ULN$ if $ULN \geq 0.5$ GIGA/L. When ULN is missing, the value 0.5 should be used.

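### The planned eGFR table has five on-treatment classes but at most two baseline groups, so new mild-to-moderate decline shares a cell with moderate impairment already present at entry

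*SAP*

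**What the plan says.** SAP 2.4.5.4 tabulates potentially clinically significant abnormalities (PCSAs) at any time on treatment. For eGFR, "the classification according to Food and Drug Administration (FDA) guidance published on March 2010 will be used as the PCSA criterion". The classes are end-stage (<15), severe (15 to <30), moderate (30 to <60), mild (60 to <90) and normal (≥90).

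The baseline rule is shared by all laboratory parameters except calcitonin and the albumin/creatinine ratio. Counts are given "whatever the baseline level and/or according to the following baseline status categories", and there are two categories: normal or missing, and "Abnormal according to PCSA criterion or criteria". Where a parameter has several criteria, the patient is counted once, "under the worst/maximum PCSA category". On missing values, SAP 2.5.3 states: "If a patient has a missing baseline he will be grouped in the category" that also holds normal baselines.

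The summaries are produced by arm for the 26-week period and for the FRC group alone over the whole study.

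Protocol 7.2.1 (E 18) excludes a "Patient who has renal function impairment with estimated glomerular filtration rate (GFR) <30", so mild and moderate impairment can be present at entry. SAP 2.1.1 tabulates "eGFR categories at screening" but does not cross them with the on-treatment class. Protocol 11.4.6.3 allows laboratory shift tables as an option; SAP 2.4.5.4 commits to none for eGFR.

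**The concern.** A safety table of worst on-treatment class is read as showing what happened on treatment. With a graded criterion and a two-way baseline, it partly shows who was enrolled. A patient stable at 45 and a patient who falls from 85 to 45 are both recorded as abnormal at baseline with moderate as worst class.

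At stake is how readable one renal table is. In the 26-week comparison, a difference between arms in new mild-to-moderate decline would look smaller as a ratio than it is. In the FRC-only summary to Week 52, the moderate row could not be read as new decline at all.

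**Working it through.** **Which cells are mixed.** Take abnormal to mean any class below 90, with eGFR below 30 excluded at entry.

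- Normal/missing baseline: every count below 90 is a new fall, apart from missing baselines. These should be rare, because chemistry is drawn at both V1 and V3 and baseline is the last value before the first injection.
- Abnormal baseline, worst class severe or end-stage: a new fall, unless eGFR dropped below 30 between screening and baseline.
- Abnormal baseline, worst class mild: stable mild, or improved moderate. No new decline.
- Abnormal baseline, worst class moderate: stable moderate plus new falls from mild. **This is the only mixed cell in the split table.**
- No baseline split, as the and/or wording permits: the mild and moderate rows are both mixed.

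If abnormal instead meant below 60, patients with mild impairment would join the normal group. The mixing would then move to the mild row of that group, where stable mild and new falls from ≥90 meet.

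**Size.** The plan states no eGFR figure. Only the 250 per group in SAP 1.3 is used, as a denominator. It reproduces: an effective difference of 0.4 × 0.8 = 0.32 and SD 1.1 give 2 × (1.960 + 1.282)² × 1.1² / 0.32², just over 248, so 249 by the normal approximation and 250 with the t distribution.

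Everything else here is assumed: 40% or 50% mild at entry (m), 5% to 30% moderate at entry (d), 95% of those moderate at entry still having moderate as worst class, and new mild-to-moderate decline in 5% of control and 10% of FRC patients (p), a true ratio of 2.0.

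Percentage in the mixed cell = (250·m·p + 250·d·0.95) / (250·(m + d)).

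Example, m = 40%, d = 10%: control (5 + 23.75)/125 = 23.0%; FRC (10 + 23.75)/125 = 27.0%; ratio 1.17.

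| Mild at entry | Moderate at entry | FRC | Control | Difference (points) | Ratio |
|---|---|---|---|---|---|
| 40% | 5% | 19.4% | 15.0% | 4.4 | 1.30 |
| 40% | 10% | 27.0% | 23.0% | 4.0 | 1.17 |
| 40% | 20% | 38.3% | 35.0% | 3.3 | 1.10 |
| 40% | 30% | 46.4% | 43.6% | 2.9 | 1.07 |
| 50% | 5% | 17.7% | 13.2% | 4.5 | 1.34 |
| 50% | 10% | 24.2% | 20.0% | 4.2 | 1.21 |
| 50% | 20% | 34.3% | 30.7% | 3.6 | 1.12 |
| 50% | 30% | 41.9% | 38.8% | 3.1 | 1.08 |

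With baseline class shown separately, the mild row reads 10% against 5%, a difference of 5.0 points and a ratio of 2.0. Other rates give the same pattern: 6% against 3% (true ratio 2.0) appears as 1.04 to 1.24, and 15% against 5% (true ratio 3.0) as 1.13 to 1.69.

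**What does not change.** The expected excess of FRC patients is 250 × m × 0.05 = 5.0 (m = 40%) or 6.25 (m = 50%) in either layout. The mixed cell does add noise from entry numbers. If 10% enter at 30 to <60, the between-arm difference in that entry count has a standard deviation of about √(2 × 250 × 0.10 × 0.90) = 6.7 patients, larger than the excess itself.

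**The case against.** Much of the case against stands.

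- A reader might infer that the table cannot show any fall among patients already below 90. That is not so: falls to below 30, the most serious ones, are visible in both baseline groups.
- A reader might also infer that a true renal signal would be lost. The documents do not support that. Randomization balances entry impairment in expectation, so the expected excess count survives, and SAP 2.4.5 plans no safety tests, so no power or error rate is at risk.
- The same section plans change-from-baseline statistics for all laboratory parameters, and a listing of each patient with a post-baseline PCSA showing the full renal profile. A fall from 85 to 45 can be seen there. Creatinine is summarized separately.
- Protocol 10.6.6 concerns acute creatinine rises during nausea and vomiting. It does not make this table the tool for that concern.
- SAP Appendix A, which holds the PCSA list, is not in the text available to me, so a further eGFR rule there cannot be ruled out.

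These outputs help, but none counts decliners by arm. Means absorb a minority: if each extra decliner lost 30 mL/min/1.73 m² (assumed), the arm means would differ by 0.40 × 0.05 × 30 = 0.6. The listing would include every stable patient below 90 if those classes count as PCSAs. The SAP 2.1.4.4 list of renal variables names creatinine clearance and not eGFR. In the FRC-only summary the randomization argument is unavailable.

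**Conclusion.** The point holds in a narrow form. If abnormal means any class below 90, one cell of the split table mixes stable moderate impairment with new mild-to-moderate decline. If the split is dropped, the mild and moderate rows are both mixed.

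The effect is on percentages and ratios in those cells: a true ratio of 2.0 appears as about 1.07 to 1.34, and a 5.0-point difference as 2.9 to 4.5 points, under the assumed entry shares and decline rates. The expected excess count is unaffected. The case is clearest for the FRC-only whole-study summary, where new mild-to-moderate decline cannot be separated from entry impairment in this table.

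It would go too far to say that the table mostly reproduces the entry distribution, because the documents give no such distribution. This is a worthwhile improvement to a descriptive table; no conclusion of the trial depends on it.

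**What to change.** In SAP 2.4.5.4, for eGFR only, replace the two-group baseline split with a table of baseline class by worst on-treatment class:

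- Baseline rows: <30 (if any), 30 to <60, 60 to <90, ≥90, and missing as a row of its own.
- Take baseline as the last value before the first injection, as in SAP 2.5.4, and not the screening class.
- Show it per arm for the 26-week period, and for FRC over the whole study.
- Report the number and percentage of patients falling by at least one class.

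The cost is one table shell. The class limits are already defined, and sample size and efficacy analyses are untouched. The drawback is that patients near a class limit can shift by chance. That should affect both arms similarly over 26 weeks; in the FRC-only table there is no second arm, so some one-class falls there will be chance and should be described that way.

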2.4.5.5 Analyses of vital sign variables

Descriptive statistics (N, mean, median, SD, minimum, and maximum) will be used to summarize results and change from baseline of all vital sign parameters. The summaries will be provided by treatment group for the 26-week randomized treatment period and for FRC group for the whole study treatment period including the 26-week single-arm extension period, respectively.

Summary statistics will be presented using baseline values, observed values from scheduled visits, and last on-treatment value. Mean value (\pm SE) at each scheduled visit will be plotted in each treatment group.

Number (%) of patients with PCSAs (see [Appendix A](#)) at any time during the on-treatment period will be summarized by treatment group for each vital sign parameter.

All measurements collected during the on-treatment period of the whole study, including values from unscheduled visits, will be considered for the PCSA summaries. The summaries will include patients in the safety population who have at least 1 assessment performed during the on-treatment period of the whole study. When a PCSA definition involves a change from baseline value, patients must also have a baseline value to be included in the summaries.

A listing of patients with at least 1 post-baseline PCSA will be provided and will display the patient's profile over time of all vital sign parameters. Individual data listings will include the following flags:

- Baseline values will be flagged "B",
- Parameter values reaching a PCSA limit will be flagged (+, or - depending of the direction).

The PCSA summaries and descriptive statistics of vital sign parameters will also be presented separately for the post-treatment period.

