9.2.2 Safety endpoints

The safety endpoints are assessed by:

- Symptomatic hypoglycemia (documented, probable, severe symptomatic hypoglycemia);
- Adverse events (AE), serious adverse events (SAE); adverse event of special interest (AESI), AEs requiring specific monitoring and reporting on specific electronic case report forms (e-CRFs) (suspected allergic reactions, patients with increased pancreatic enzymes >2 ULN/pancreatic events, patients with increased calcitonin ≥ 20 pg/mL, Device-related events (DRE));
- Safety laboratory values;
- Vital signs;
- Electrocardiogram (ECG);
- Immunogenicity (antibody variables, FRC group): anti-insulin and anti-lixisenatide antibodies.

Observation period of safety endpoints

The observation period of safety data will be divided into 3 segments:

- The pre-treatment period is defined as the time between the date of the informed consent and the first injection of open-label IMP;
- The 26-week on-treatment period is defined as follows:
 - For patients who are not eligible to enter the extension period, the 26-week on-treatment period is defined as:
 - For patients receiving daily IMP: time from the first injection of open-label daily IMP up to 3 days (1 day for symptomatic hypoglycemia) after the last injection of daily IMP, regardless of the introduction of rescue therapy;
 - For patients receiving weekly IMP: from the first injection of open-label weekly IMP up to 9 days (7 day for symptomatic hypoglycemia) after the last injection of weekly IMP, regardless of the introduction of rescue therapy.
 - For the patients who are eligible to enter the extension period, on-treatment period is defined as time from the first injection of open-label IMP up to V28/Week 26 visit (or Day 183 if V28/Week 26 visit is missing).
- The on-treatment period for the whole study (including the 26-week extension period) is defined as the time from the first injection of open-label IMP up to 3 days (1 day for symptomatic hypoglycemia) after the last injection of IMP, regardless of the introduction of rescue therapy. For patients who are not eligible to enter the extension period, the on-treatment period for the whole study is the 26-week on-treatment period.

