2.1.4 Safety endpoints

The safety endpoints are assessed by:

- Symptomatic hypoglycemia (documented, probable, severe symptomatic hypoglycemia),
- Adverse events (AEs), serious adverse events (SAEs), and AE of special interest (AESI),
- Safety laboratory values,
- Vital signs,
- Electrocardiogram (ECG).
- Immunogenicity (antibody variables, FRC group): anti-insulin and anti-lixisenatide antibodies.

Observation period

The observation period of safety data will be divided into 3 segments:

- The pre-treatment period is defined as the time between the date of the informed consent and the first injection of open-label IMP,
- The on-treatment period of the whole study for daily formulation is defined as the time from the first injection of open-label IMP up to 3 days (1 day for symptomatic hypoglycemia) after the last injection of IMP, regardless of the introduction of rescue

therapy. The on-treatment period of the whole study for weekly formulation is defined as the time from the first injection of open-label IMP up to 9 days (7 day for symptomatic hypoglycemia) after the last injection of IMP, regardless of the introduction of rescue therapy.

- The 26-week on-treatment period is defined as follows:
 - For patients who are not eligible to enter the extension period, the 26-week on-treatment period is defined as
 - For patients receiving daily IMP: time from the first injection of open-label daily IMP up to 3 days (1 day for symptomatic hypoglycemia) after the last injection of daily IMP, regardless of the introduction of rescue therapy.
 - For patients receiving weekly IMP: time from the first injection of open-label weekly IMP up to 9 days (7 day for symptomatic hypoglycemia) after the last injection of weekly IMP, regardless of the introduction of rescue therapy.
 - For the patients who are eligible to enter the extension period, the 26-week on-treatment period is defined as the time from the first injection of open-label IMP up to V28/Week 26 visit (or Day 183 if V28/Week 26 visit is missing).
- The post-treatment period is defined as the time starting 4 days (2 days for symptomatic hypoglycemia) after the last injection of open-label daily IMP, or starting 10 days (8 days for symptomatic hypoglycemia) after the last injection of open-label weekly IMP (after the on-treatment period of the whole study).

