2.4.5 Analyses of safety data

The summary of safety results will be presented by treatment group for the 26-week randomized treatment period, unless specified otherwise. A similar summary of safety results will also be presented for FRC group for the whole study treatment period including the 26-week single-arm extension period, as appropriate.

The “observation period” defined in [Section 2.1.4](#) are applicable for classification of AEs, (potentially clinically significant abnormality) PCSA values for the laboratory and vital sign.

General common rules

All safety analyses will be performed on the safety population as defined in [Section 2.3.2](#), unless otherwise specified, using the following common rules:

- Safety data in patients who do not belong to the safety population (eg, exposed but not randomized) will be listed separately;
- The baseline value is defined as the last available value before the first injection of open-label IMP. For WBC and differential counts, the baseline will be defined as the last available value before the first injection of open-label IMP where no differential component is missing;
- The PCSA values are defined as abnormal values considered medically important by the Sponsor according to predefined criteria/thresholds based on literature review and defined by the Sponsor for clinical laboratory tests, vital signs, and ECG (PCSA version dated May 2014 [[Appendix A](#)]). PCSA criteria for parameters not cited in the protocol as safety parameters will not be analyzed;
- PCSA criteria will determine which patients had at least 1 PCSA during the specified period, taking into account all evaluations performed during the specified period, including unscheduled or repeated evaluations. The number of all such patients will be the numerator for the PCSA percentage during the specified period;
- The treatment-emergent PCSA denominator by group for a given parameter will be based on the number of patients assessed for that given parameter during the specified period by treatment group in the safety population;

- For laboratory parameters cited in the protocol as efficacy endpoints (including HbA1c and plasma glucose), PCSA summaries will not be provided. These parameters will be summarized in [Section 2.4.4](#);

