2.4.5.6 Analyses of electrocardiogram variables

- Shift tables will be provided to present ECG status according to baseline status (Normal/Missing, Abnormal) for each treatment group during the 26-week on-treatment period and for FRC group during the on-treatment period of the whole study. Supportive listings of patients with abnormal ECG status at any post-baseline visit will be provided.

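### SAP 2.4.5.5 puts the by-treatment vital-sign PCSA table on the whole-study period, so FRC could be counted for up to 52 weeks against 26 for control

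*SAP*

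**What the plan says.** SAP 2.4.5.5 begins with a split of periods: "The summaries will be provided by treatment group for the 26-week randomized treatment period and for FRC group for the whole study treatment period". SAP 2.4.5 sets the same default for safety results in general ("The summary of safety results will be presented by treatment group for the 26-week randomized treatment period"), but allows exceptions where another period is specified.

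The PCSA table in 2.4.5.5 then gives the number and percentage of patients with an abnormality "at any time during the on-treatment period will be summarized by treatment group for each vital sign parameter". That sentence does not say which on-treatment period it means. The next two sentences do. On the data: "All measurements collected during the on-treatment period of the whole study, including values from unscheduled visits, will be considered for the PCSA summaries". On the patients: those in the safety population "who have at least 1 assessment performed during the on-treatment period of the whole study". Neither sentence is restricted to the FRC-only table.

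The whole-study on-treatment period is a defined term. In SAP 2.1.4, "The on-treatment period of the whole study for daily formulation is defined as the time from the first injection of open-label IMP", ending 3 days after the last injection (9 days for weekly products). Protocol 9.2.2 adds: "For patients who are not eligible to enter the extension period, the on-treatment period for the whole study is the 26-week on-treatment period". Protocol 7.2.5 excludes every patient in the GLP-1 RA arm from the extension.

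**The concern.** The table reports whether a patient ever had an abnormal value in the period. Such a percentage can only stay level or rise as observation lengthens. If extending FRC patients are observed for about twice as long as controls, the FRC column can show more blood-pressure and heart-rate abnormalities with no drug effect at all.

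The conflict lies in the two sentences that decide which records and which patients enter the table, and a programmer would work from those. At stake is a fair reading of one between-group safety table. The distortion would make FRC look worse; it would not hide an FRC abnormality.

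**Working it through.** **1. The plan's own durations.** From the periods in the protocol synopsis:
- FRC: 2 + 26 + 26 weeks + 3 days = 54.4 weeks (stated as about 55).
- Control: 2 + 26 weeks + 3 or 9 days = 28.4 to 29.3 weeks (stated as about 29).

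Both reproduce, so the 52 against 26 weeks on treatment is the plan's own design.

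**2. Observation windows under the literal wording, for completers.**
- FRC patient who extends: 52 × 7 + 3 = 367 days.
- Control, daily product: 26 × 7 + 3 = 185 days.
- Control, weekly product: at most 26 × 7 + 9 = 191 days.
- Ratio: 367/191 = 1.92 to 367/185 = 1.98.

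**3. The parallel texts.**

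| Place | Period for the between-group table |
|---|---|
| SAP 2.4.5.5, opening | 26 weeks; whole study for FRC only |
| SAP 2.4.5.5, two PCSA sentences | Whole study, not limited to FRC |
| SAP 2.4.5.4, laboratory PCSA | On-treatment period, without the whole-study qualifier |
| SAP 2.4.5.6, ECG | "for each treatment group during the 26-week on-treatment period and for FRC group during the on-treatment period of the whole study" |
| Protocol 11.4.6.4, vital signs | On-treatment period, without the whole-study qualifier |

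Only the two PCSA sentences in 2.4.5.5 put a between-group table on the longer period.

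**4. Possible size.** The documents give no vital-sign PCSA rate, so this is an illustration with the same risk in both arms. Inputs:
- p, the assumed risk per 26 weeks.
- f, the share of FRC patients who extend: 0.80 (the 20% drop-out assumption in SAP 1.3, i.e. 200 of 250) to 0.92 (230 of 250, protocol synopsis).
- g, the share of the extension observed.
- Scheduled readings in the flow chart: 6 after baseline up to Week 26, and 3 more at Weeks 34, 42 and 52.

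Risk per unit of time: FRC percentage = p + f(1 − p)(1 − (1 − p)^g).
For p = 0.05, f = 0.92, g = 1: 0.05 + 0.92 × 0.95 × 0.05 = 0.0937.

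Risk per scheduled reading, full follow-up: FRC percentage = (1 − f)p + f(1 − (1 − p)^1.5), where 1.5 = 9/6.
For p = 0.05, f = 0.92: 0.004 + 0.92 × 0.0741 = 0.0721.

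| Assumed 26-week risk (control) | FRC, per reading | FRC, per unit of time |
|---|---|---|
| 2% | 2.8–2.9% | 3.6–3.8% |
| 5% | 6.9–7.2% | 8.8–9.4% |
| 10% | 13.7–14.2% | 17.2–18.3% |

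The ranges run from f = 0.80 to f = 0.92, with complete 52-week follow-up.

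SAP Section 4 plans a first lock about 4 weeks after the last 26-week visit, when extension follow-up is only partial. With p = 5% and the time formula, g = 0.5 gives 6.9–7.2%, g = 0.25 gives 6.0–6.1%, and g = 0 gives 5%. Both formulas assume that first abnormalities continue at the same rate after Week 26. If they do not, the excess shrinks towards zero.

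**5. After correction.** With the 26-week on-treatment period, an extending FRC patient is cut at the Week 26 visit (or Day 183 if that visit is missing), against about 185 to 191 days for a control completer. The windows are then nearly equal.

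**The case against.** The strongest reply is that the rest of the plan makes the intention clear. SAP Section 3, like Protocol 6.3 and 11.5, bases the primary safety analysis on the 26-week randomized period. The general rules in SAP 2.4.5 tie the PCSA numerator and denominator to whatever period has been specified, and the opening of 2.4.5.5 specifies it. The two later sentences could then be read as describing the pool of data for both tables, with each table's period fixed by the opening paragraph. On the literal reading, the FRC column would merely repeat the FRC-only table. Appendix C, a summary of the analyses listed in the SAP's contents, was not in the text available here and may name the period.

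Much of this stands: 26 weeks is probably what was meant. It does not remove the conflicting rule. The default in 2.4.5 yields where another period is specified, and these sentences specify one. If the opening paragraph is taken to cover only the descriptive statistics, the contradiction weakens, but the whole-study period is then the only one named for the PCSA table. If Appendix C says 26 weeks, the body text would still disagree with it.

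The objection is also right that the harm is limited. SAP 2.4.5 plans no testing of safety variables, by-visit statistics still compare the arms at matched visits, and the patient listings show when each abnormality occurred.

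**Conclusion.** The concern holds. As written, SAP 2.4.5.5 gives two different periods for the same table, and following the PCSA sentences would produce a between-group percentage with unequal follow-up: 1.92 to 1.98 times as long for an extending FRC completer as for a control completer. That the text conflicts is certain; that the longer period would actually be programmed is less so.

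The size cannot be fixed from the documents. At an assumed equal 5% risk, the excess for FRC runs from zero to 4.4 percentage points (9.4 − 5.0), depending on extension follow-up and on whether first abnormalities continue after Week 26. The consequence is confined to one descriptive safety table and touches no efficacy conclusion. It should be corrected before programming.

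**What to change.** In both PCSA sentences of SAP 2.4.5.5 (the one on measurements and the one on patients included), name the 26-week on-treatment period for the table by treatment group. State that the whole-study on-treatment period applies only to the separate FRC-only table, in the form SAP 2.4.5.6 already uses for ECG. Check that Appendix C agrees.

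The cost is two phrases in the SAP. No new data are needed and nothing is lost, because the FRC-only whole-study table remains.
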